#### 4.9. Clinically Relevant Diseases

The following are considered as clinically relevant diseases:

- Hospitalization (as collected on eCRF AE pages (linked via acute respiratory infection form or complications linked to ARI form), medical encounters [Intensive Care Unit and Hospital inpatient department] form and MRU pages [Emerging Hospitalization admissions-Section 4.11])
- Emergency Department visit (as assessed on the eCRF medical encounters form and MRU pages)
- X-ray confirmed pneumonia (as assessed on the eCRF diagnostic tests form: diagnosis of pneumonia confirmed by chest X-ray)
- Radiological confirmed pneumonia (as assessed on the eCRF diagnostic tests form: diagnosis of pneumonia confirmed by chest X-ray, CT-scan or MRI)
- Oxygen saturation < 90% (as indicated on the clinical assessment form)
- Supplemental oxygen (as indicated on the eCRF medical encounters form and the eCRF oxygen supplementation form)
- Exacerbation of disease (COPD and Asthma) (as captured under the eCRF diagnostic tests pages and the pages on measurements during a medically attended ARI)
- Pulmonary function test results supporting diagnosis of LRTD (as captured under the eCRF pages on measurements during a medically attended ARI, where peak expiratory flow, spirometry FVC, FEV1 or FEV6 are indicated as well as that the measurement is clinically significant and supports LRTD)

- Arterial blood gas results supporting diagnosis of LRTD (as captured under the eCRF pages on measurements during a medically attended ARI, where arterial blood gas pH, PaO2, PaCO2, HC03 or oxygen saturation are indicated as well as that the measurement is clinically significant and supports LRTD)

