#### **4.11. Medical Resources Use Questionnaire**

Medical resource utilization questionnaire data are collected at baseline and during an ARI episode at Day 3-5 and Day 29. The questionnaire contains 4 categories of medical resources and each of them has several subcategories (see [Attachment 10](#) in CTP).

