##### **4.11.1. Analysis Methods**

The PPE set will be used to analyze the medical resource utilization data.

At baseline the proportion of participants reporting having used the medical resources by category and subcategory will be summarized per group and per risk level.

For participants with any RT-PCR confirmed RSV the proportion of those reporting having used the medical resources by category and subcategory will be summarized per group and per risk level. The number of recorded visits and the length of stay will also be summarized descriptively.

In case two or more assessments are reported at the same day (for example two assessments at the same device) then the worst score per question will be used.

Finally, emerging medical resources utilized during an ARI episode will be summarized per group for all ARI cases, for all RT-PCR confirmed RSV cases, for all negative (or missing) RT-PCR RSV cases and for the 3 case definitions. A treatment - emergent medical resource is defined as a medical resource visit that was related to an ARI or a complication of an ARI (meaning the ‘Specify number of visits related to ARI or its complications’ question in the MRU is equal or larger to one).

In case a participant experiences two or more ARIs (based on the ‘Any ARI’ definition, Section 4.4.3.1) during the study then the following rules will be followed in identifying which ARIs data will be used:

- If all fulfil a case definition, then data from the RT-PCR confirmed RSV disease fulfilling the strictest definition will be used (case definition 1 > case definition 2 > case definition 3)
- If only one fulfils a case definition, then those data will be used
- If none fulfils a case definition or all fulfil the same case definition, then data from the first RT-PCR confirmed RSV disease will be used.
- If none is a RT-PCR confirmed RSV-disease, then use:
  - the ARI that fulfils the strictest case definition based on symptoms only (case definition 1 > case definition 2 > case definition 3) Or
  - the first ARI, in case 2 or more fulfil the same case definition on symptoms only or in case they do not fulfil any case definition on symptoms only.

Note: For outputs were only planned visits (ARI Day 3-5, ARI Day 29, End of season) are presented, the worst across the different scheduled and unscheduled visits will be presented per visit.

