## 5.8. Clinically Relevant Diseases

Clinical relevant diseases associated with RSV ARIs as defined in the phase 3 VAC18193RSV3001 study will be analyzed:

- Hospitalization
- Emergency department visit (as assessed on the eCRF medical encounters form and MRU pages [emerging MRU to be summarized])
- At least one of the following complications: asthma, COPD, respiratory distress, bronchitis, bronchial hyperreactivity, CHF, cardiac arrhythmia, renal impairment or the presence of X-ray or radiological confirmed pneumonia, respiratory arrest and/or failure, pulmonary embolism, pleural effusion, atelectasis, acute coronary events, acute cerebrovascular events, altered mental status, seizure, syncope, systemic inflammatory response syndrome (SIRS), new neurological deficit, asthenia, dehydration or metabolic disturbances.  
See [Attachment 10](#) for the complication terms. These terms will be reported in the AE domain.  
Asthma and chronic obstructive pulmonary disease (COPD) exacerbation supporting LRTD reported in the medically attended ARI form will also be counted, as well as X-ray or radiological confirmed pneumonia from the diagnostic tests form.
- Decreased oxygen saturation defined as oxygen saturation of <92% for participants with a baseline oxygen saturation of  $\geq 92\%$  at randomization; for participants with baseline oxygen saturation <92%, decreased oxygen saturation is defined as a  $\geq 3\%$  decrease in their oxygen saturation from baseline
- Tachypnea (at least Grade 2, see Section 4.8)
- Need of supplemental oxygen
- Hypotension (at least Grade 3, see Section 4.8)
- Pulmonary function test results supporting diagnosis of LRTD
- Arterial blood gas results supporting diagnosis of LRTD

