### 5.8.1. Analysis Methods

The PPE set will be used to analyze all clinically relevant diseases.

For the second and third RSV season and across season two and three and across all three RSV seasons, the following will be calculated. The proportion of participants with any RT-PCR confirmed RSV disease leading to clinically relevant diseases (as defined in Section 4.9 and 5.8) leading to clinically relevant diseases will be tabulated per group and the corresponding VE (1-relative risk) with a 95% CI will be determined and graphically depicted with a forest plot. A Poisson model similar to the primary endpoint will be used.

Any RT-PCR confirmed RSV disease leading to clinically relevant diseases as defined in Section 5.8 will also be summarized for the first RSV season.

The different subcategories of the clinically relevant diseases will be summarized only across the three RSV seasons, for participants with any RT-PCR confirmed RSV disease and RT-PCR-confirmed RSV-mediated LRTD based on Case Definition 1.

In case a participant experiences two or more RSV ARIs during the three RSV seasons, the same rule will apply similar to a participant experiencing two or more ARIs during the same season (see Section 4.5.1.1).

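### The emergency-visit item in SAP Section 4.9 takes visits from the MRU pages without the ARI-related (emerging) limit that its neighbouring hospitalisation item and the Section 5.8 version both carry

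*SAP*

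**What the plan says.** SAP Section 4.9 defines clinically relevant disease as a list of items with their data sources. Two adjacent items draw on the MRU questionnaire:

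- Hospitalisation, where the MRU source is restricted: "MRU pages [Emerging Hospitalization admissions-Section 4.11".
- Emergency visit, where it is not: "Emergency Department visit (as assessed on the eCRF medical encounters form and MRU pages".

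Section 4.11.1 supplies the meaning of emerging: "A treatment - emergent medical resource is defined as a medical resource visit that was related to an ARI or a complication of an ARI". It is decided by whether the participant reports at least one visit related to the ARI or its complications.

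Section 5.8, the version aligned with the phase 3 study, repeats the emergency-visit item with the restriction: "Emergency department visit (as assessed on the eCRF medical encounters form and MRU pages [emerging MRU to be summarized".

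The Section 4.9 list feeds the season 1 VE analysis (4.9.1) and the placebo association analyses (4.9.2). It also feeds the VE analyses for season 2, season 3, seasons 2 and 3 together, and all three seasons, since Section 5.8.1 refers to disease "leading to clinically relevant diseases (as defined in Section 4.9 and 5.8".

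**The concern.** The MRU questionnaire records resource use in general and asks separately how much of it was ARI-related, so it can hold an emergency visit with zero ARI-related visits. Under Section 4.9 nothing stops such a visit, for an injury for example, from making an RSV-positive participant a case of clinically relevant RSV disease. Under Section 5.8 the same MRU record would not count.

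At stake are the VE estimate against clinically relevant RSV disease, the odds ratios that relate the case definitions to clinically relevant disease in placebo participants, and whether the Section 4.9 and 5.8 results can be compared.

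**Working it through.** The SAP states no event count or VE for this endpoint, so there is no figure to reproduce. The check is a comparison of the text, followed by the direction of any bias.

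**1. Is the limit missing, or only placed elsewhere?**

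| Item | MRU source limited to emerging use? |
|---|---|
| 4.9 hospitalisation | Yes, with reference to Section 4.11 |
| 4.9 emergency visit | No |
| 5.8 emergency visit | Yes |

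The limit is written item by item. No general statement in Section 4.9 or 4.9.1 extends it to the whole list.

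**2. Can the MRU hold unrelated visits?** Yes. Section 4.11.1 needs a separate criterion, a "medical resource visit that was related to an ARI or a complication of an ARI", to pick out emerging use. If every recorded visit were ARI-related, the criterion would have no purpose.

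**3. Does timing supply the link?** Only in part. According to Section 4.11, "Medical resource utilization questionnaire data are collected at baseline and during an ARI episode at Day 3-5 and Day 29". Records after baseline are therefore close in time to an ARI, but that does not make the visit related to it.

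**4. Does Section 5.8.1 remove the problem in later seasons?** No, on either reading. If the two definitions are combined, the open 4.9 item overrides the limit in 5.8. If they are analysed separately, the 4.9 analysis still has the open item.

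**5. Direction of bias in VE.** For RSV-confirmed ARIs, let:

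- c = share of placebo RSV ARIs with true clinically relevant disease;
- q = share of the remaining RSV ARIs that have only an unrelated emergency visit, assumed equal in both arms;
- RR_C = relative risk of true clinically relevant RSV disease;
- RR_A = relative risk of any RSV ARI.

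Per placebo RSV ARI, counted events are c + (1 − c)q in the placebo arm and c·RR_C + (RR_A − c·RR_C)q in the vaccine arm. Their ratio rearranges to

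RR_obs = [c(1 − q)·RR_C + q·RR_A] / [c(1 − q) + q].

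This is a weighted average of RR_C and RR_A. It equals RR_C when q = 0 and moves toward RR_A as q grows. If RR_C = RR_A it does not depend on q. The pull is therefore toward VE against any RSV ARI, not toward zero. The SAP gives none of c, q, RR_C or RR_A, so the amount cannot be calculated.

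**6. Direction in Section 4.9.2.** Let o1 and o0 be the true odds of clinically relevant disease among placebo participants meeting and not meeting a case definition. If unrelated visits are equally likely (q) in both groups, the observed odds are (o + q)/(1 − q), and the observed odds ratio is (o1 + q)/(o0 + q). This is closer to one than o1/o0. The any-ARI subgroup is exposed as well as the RSV-confirmed one.

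**The case against.** The strongest reply is that Section 4.9.1 counts only RT-PCR confirmed RSV disease leading to a clinically relevant disease, and Section 4.9.2 uses similar wording. An injury visit does not meet that wording. A reader might infer from the open item that every emergency visit becomes an RSV event, and the documents do not support that. What stands against the reply is that no rule says how the causal link is decided. The authors also wrote an explicit limit for hospitalisation in 4.9 and for emergency visits in 5.8, so they did not rely on the general wording there.

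The plan can also be read as two separate analyses under two named definitions, and Section 5.8.1 adds a season 1 summary under the 5.8 definition. That is fair: a conflict inside a single VE analysis is possible but not shown. The 5.8 summary is not a substitute, however, because that list differs from 4.9 in several other items.

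A reader might extend the point to oxygen, since Section 4.9 has "Supplemental oxygen (as indicated on the eCRF medical encounters form and the eCRF oxygen supplementation form" with no reference to earlier use. The documents do not support this as a departure from a rule. No new-use rule for oxygen appears anywhere in the SAP. Section 5.8 asks only whether supplemental oxygen was needed, and the new-or-increased rule in Section 4.10 covers medication classes. Nor does the SAP show whether the oxygen and medical encounters forms are already ARI-specific or record use before the ARI. For the same reason, the present point is confined to the MRU pages and does not extend to emergency visits from the medical encounters form.

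**Conclusion.** The point holds as a gap in one source of one item. The emergency-visit item in Section 4.9 lacks the emerging limit, and unrelated visits on the MRU can be counted in the analyses of Sections 4.9.1, 4.9.2 and 5.8.1 that use that definition.

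The consequence is bounded. Only non-primary analyses are affected; the primary endpoints and the proof-of-concept decision do not use this list. The directions derived above rest on unrelated visits being equally frequent in the groups compared. A reader might want a number for the loss in VE, but any such number would rest wholly on assumed inputs, so none is given. The gap is still worth closing, because the plan already contains the rule and the field needed to apply it.

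**What to change.** In Section 4.9, add to the emergency-visit item that MRU visits count only if emerging as defined in Section 4.11, matching the hospitalisation item and Section 5.8. State that the limit applies in every analysis using the 4.9 definition: 4.9.1, 4.9.2, and the season 2, season 3, combined season 2 and 3, and three-season analyses in 5.8.1.

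Section 1.6 describes the season 1 primary analysis in the past tense. If the season 1 table was produced without the limit, footnote it or show it both ways, so that the change of definition is visible.

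The cost is one line of text and a filter on the ARI-related visit count that the MRU already collects. The downside is a possibly slightly lower event count.

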#### 4.9.1. Analysis Methods

The PPE set will be used to analyze all clinically relevant diseases.

The proportion of participants with any RT-PCR confirmed RSV disease leading to clinically relevant diseases and those with RT-PCR-confirmed RSV-mediated LRTD based on the 3 case definitions leading to clinically relevant diseases will be tabulated per group and the corresponding VE (1-relative risk) with an exact Poisson 95% 2-sided CI will be determined and graphically depicted with a forest plot similar to the primary analysis

Depending on their occurrence, the above might be repeated for the different subcategories of clinically relevant disease (with or without calculation of VE).

#### 4.9.2. The Relationship Between the Primary Endpoints and Clinically Relevant Disease

In order to establish the interrelationship between the primary endpoints and clinically relevant diseases, the following analyses will be performed restricted to the placebo group. These analyses will be performed in two subgroups of the PPE set:

- participants with any RT-PCR confirmed RSV disease (see [above](#) for definition)
- participants with any ARI (see [Any ARI](#) definition, independently of RSV etiology)

In each of those subgroups the following will be calculated: the percentage of subjects having an (RT-PCR confirmed RSV) ARI leading to clinically significant disease will be shown for:

- participants meeting Case Definition 1 versus participants not meeting any Case Definition
- participants meeting Case Definition 2 (or 1) versus participants not meeting any Case Definition
- participants meeting Case Definition 3 (or 1 or 2) versus participants not meeting any Case Definition

The corresponding odds ratio (and 95% CI) will be shown as well

In case of limited number of participants not meeting any case definition:

- participants meeting Case Definition 1 versus participants not meeting Case Definition 1
- participants meeting Case Definition 2 (or 1) versus participants not meeting Case Definition 2 (or 1)
- participants meeting Case Definition 3 (or 1 or 2) versus participants not meeting any Case Definition

The corresponding odds ratio (and 95% CI) will be shown as well

Note: In case a participant experiences two or more ARIs during the study the same rule as for the RiiQ will be used.

Depending on their occurrence, the above might be repeated for the different subcategories of clinically relevant disease or for subgroups.

As a sensitivity check the same analysis will be performed but without taking into account cough for any of the case definitions.

#### **4.10. Therapeutic Interventions**

The following are considered as therapeutic interventions of interest:

- New/increased bronchodilator/nebulizer treatment
- New/increased corticosteroid prescription
- New/increased antibiotic prescription
- New/increased antiviral prescription

These will be taken from the concomitant medication pages of the eCRF based on [Attachment 5](#).

The ones linked to an ARI or complication of an ARI will be displayed.

##### **4.10.1. Analysis Methods**

The PPE set will be used to analyze the use of therapeutic interventions.

Therapeutic interventions taken at baseline will be summarized for all subjects in the PPE set.

Moreover, the proportion of participants with any RT-PCR confirmed RSV disease utilizing new therapeutic interventions and those with RT-PCR-confirmed RSV-mediated LRTD based on the 3 case definitions utilizing new therapeutic interventions will be tabulated per group and the corresponding VE (1-relative risk) with an exact Poisson 95% 2-sided CI will be determined and graphically depicted with a forest plot, similar to the primary analysis.

Baseline and new interventions are defined as in Section [4.1.4](#).

Depending on their occurrence, the above might be repeated for the different subcategories of therapeutic interventions or for subgroups (with or without calculation of VE).

##### **4.10.2. The Relationship Between the Primary Endpoints and Use of Therapeutic Interventions**

In order to establish the interrelationship between the primary endpoints and use of therapeutic interventions, the following analyses will be performed restricted to the placebo group. These analyses will be performed on two subgroups of the PPE set:

- participants with any RT-PCR confirmed RSV disease (see [above](#) for definition)
- participants with any ARI (see [Any ARI](#) definition, independently of RSV etiology)

In each of those subgroups the following will be calculated: the percentage of subjects having an (RT-PCR confirmed RSV) ARI utilizing new therapeutic interventions will be shown for:

- participants meeting Case Definition 1 versus participants not meeting any Case Definition
- participants meeting Case Definition 2 (or 1) versus participants not meeting any Case Definition
- participants meeting Case Definition 3 (or 1 or 2) versus participants not meeting any Case Definition

The corresponding odds ratio (and 95% CI) will be shown as well.

In case of limited number of participants not meeting any case definition:

- participants meeting Case Definition 1 versus participants not meeting Case Definition 1
- participants meeting Case Definition 2 (or 1) versus participants not meeting Case Definition 2 (or 1)
- participants meeting Case Definition 3 (or 1 or 2) versus participants not meeting any Case Definition

The corresponding odds ratio (and 95% CI) will be shown as well.

Note: In case a participant experiences two or more ARIs during the study the same rule as for the RiiQ will be used.

Depending on their occurrence, the above might be repeated for the different subcategories of therapeutic interventions.

As a sensitivity check the same analysis will be performed but without taking into account cough for any of the case definitions.

#### **4.11. Medical Resources Use Questionnaire**

Medical resource utilization questionnaire data are collected at baseline and during an ARI episode at Day 3-5 and Day 29. The questionnaire contains 4 categories of medical resources and each of them has several subcategories (see [Attachment 10](#) in CTP).

##### **4.11.1. Analysis Methods**

The PPE set will be used to analyze the medical resource utilization data.

At baseline the proportion of participants reporting having used the medical resources by category and subcategory will be summarized per group and per risk level.

For participants with any RT-PCR confirmed RSV the proportion of those reporting having used the medical resources by category and subcategory will be summarized per group and per risk level. The number of recorded visits and the length of stay will also be summarized descriptively.

In case two or more assessments are reported at the same day (for example two assessments at the same device) then the worst score per question will be used.

Finally, emerging medical resources utilized during an ARI episode will be summarized per group for all ARI cases, for all RT-PCR confirmed RSV cases, for all negative (or missing) RT-PCR RSV cases and for the 3 case definitions. A treatment - emergent medical resource is defined as a medical resource visit that was related to an ARI or a complication of an ARI (meaning the ‘Specify number of visits related to ARI or its complications’ question in the MRU is equal or larger to one).

In case a participant experiences two or more ARIs (based on the ‘Any ARI’ definition, Section 4.4.3.1) during the study then the following rules will be followed in identifying which ARIs data will be used:

- If all fulfil a case definition, then data from the RT-PCR confirmed RSV disease fulfilling the strictest definition will be used (case definition 1 > case definition 2 > case definition 3)
- If only one fulfils a case definition, then those data will be used
- If none fulfils a case definition or all fulfil the same case definition, then data from the first RT-PCR confirmed RSV disease will be used.
- If none is a RT-PCR confirmed RSV-disease, then use:
  - the ARI that fulfils the strictest case definition based on symptoms only (case definition 1 > case definition 2 > case definition 3) Or
  - the first ARI, in case 2 or more fulfil the same case definition on symptoms only or in case they do not fulfil any case definition on symptoms only.

Note: For outputs were only planned visits (ARI Day 3-5, ARI Day 29, End of season) are presented, the worst across the different scheduled and unscheduled visits will be presented per visit.

#### **4.12. The Relationship Between the Primary Endpoints and Medical Resource Use**

In order to establish the interrelationship between the primary endpoints and medical resource utilization, the following analyses will be performed restricted to the placebo group. These analyses will be performed on two subgroups of the PPE set:

- participants with any RT-PCR confirmed RSV disease (see [above](#) for definition)
- participants with any ARI (see [Any ARI](#) definition, independently of RSV etiology).

In each of those subgroups the following will be calculated: the percentage of subjects having an (RT-PCR confirmed RSV) ARI and emerging medical resources use will be shown for:

- participants meeting Case Definition 1 versus participants not meeting any Case Definition
- participants meeting Case Definition 2 (or 1) versus participants not meeting any Case Definition
- participants meeting Case Definition 3 (or 1 or 2) versus participants not meeting any Case Definition

The corresponding odds ratio (and 95% CI) will be shown as well.

In case of limited number of participants not meeting any case definition:

- participants meeting Case Definition 1 versus participants not meeting Case Definition 1
- participants meeting Case Definition 2 (or 1) versus participants not meeting Case Definition 2 (or 1)
- participants meeting Case Definition 3 (or 1 or 2) versus participants not meeting any Case Definition

The corresponding odds ratio (and 95% CI) will be shown as well.

Note: In case a participant experiences two or more ARIs during the study the same rule as for the RiiQ will be used.

As a sensitivity check the same analysis will be performed but without taking into account cough for any of the case definitions.

